## **Events with Completely Missing Onset Date**

An AE with a completely missing onset date is defined as TEAE if end date meets any of the criteria specified in 3) above.

## 17) Graded Laboratory Abnormalities Summary

The following labels will be used for treatment-emergent laboratory abnormalities and treatment-emergent Grade 3 or 4 laboratory abnormalities summary tables and listings:

Battery	Lab Test Label Used in l-labtox Listing	Toxicity Direction	Lab Test Label Used in t-labtox Table
	Hemoglobin	Decrease	Hemoglobin (Decreased)
Hamatalasa	Neutrophils	Decrease	Neutrophils (Decreased)
Hematology	Platelets	Decrease	Platelets (Decreased)
	WBC	Decrease	WBC (Decreased)
	Albumin	Decrease	Albumin (Decreased)
	Alkaline Phosphatase	Increase	Alkaline Phosphatase (Increased)
	ALT	Increase ALT (Increased)	
	Amylase	Amylase Increase Amylase (Increased)	
	AST	Increase	AST (Increased)
Chaminto	Bicarbonate	Decrease	Bicarbonate (Decreased)
Chemistry	Corrected Calcium	Increase	Corrected Calcium (Hypercalcemia)
	Corrected Calcium	Decrease	Corrected Calcium (Hypocalcemia)
	Creatine Kinase (CK)	Increase	Creatine Kinase (Increased)
	Creatinine	Increase	Creatinine (Increased)
	Lipase	Increase	Lipase (Increased)
	Magnesium	Decrease	Magnesium (Hypomagnesemia)

Battery	Lab Test Label Used in l-labtox Listing	Toxicity Direction	Lab Test Label Used in t-labtox Table	
	Phosphate	Decrease	Phosphate (Hypophosphatemia)	
	Serum Glucose (Fasting)	Increase	Serum Glucose (Fasting, Hyperglycemia)	
	Serum Glucose (Fasting)	Decrease	Serum Glucose (Fasting, Hypoglycemia)	
	Serum Glucose (Nonfasting)	Increase	Serum Glucose (Nonfasting, Hyperglycemia)	
	Serum Glucose (Nonfasting)	Decrease	Serum Glucose (Nonfasting, Hypoglycemia)	
	Serum Potassium	Increase	Serum Potassium (Hyperkalemia)	
	Serum Potassium	Decrease	Serum Potassium (Hypokalemia)	
	Serum Sodium	Increase	Serum Sodium (Hypernatremia)	
	Serum Sodium	Decrease	Serum Sodium (Hyponatremia)	
	Total Bilirubin	Increase	Total Bilirubin (Hyperbilirubinemia)	
	Total Cholesterol (Fasting)	Increase	Total Cholesterol (Fasting, Hypercholesterolemia)	
	Triglycerides (Fasting)	Increase	Triglycerides (Fasting, Increased)	
	LDL (Fasting)	Increase	LDL (Fasting, Increased)	
	Urea Nitrogen (BUN)	Increase	Urea Nitrogen (Increased)	
	Urine Blood (Dipstick)	Increase	Urine RBC (Hematuria, Quantitative or Dipstick)*	
Urinalysis	Urine Glucose	Increase	Urine Glucose (Glycosuria)	
	Urine RBC (Quantitative)	Increase	Urine RBC (Hematuria, Quantitative or Dipstick)*	

\* Due to the reflexive nature of the quantitative urine RBC test, results will be combined with the dipstick test of urine blood as described below:

Is Post-BL Urine RBC (Quant.) Result Available?	Is BL Urine RBC (Quant.) Result Available?	Is Post-BL Urine Blood (Dipstick) Result Available?	Is BL Urine Blood (Dipstick) Result Available?	How to Determine Treatment- Emergent Toxicity for "Urine RBC (Hematuria, Quantitative or Dipstick)"
Yes	Yes	-	-	Compare post-BL Urine RBC (Quant.) toxicity grade to BL Urine RBC (Quant.) toxicity grade. If post-BL toxicity is greater than BL toxicity, then treatment-emergent
Yes	No	-	-	Treatment-emergent. Use post-BL Urine RBC (Quant.) toxicity grade.
No	-	Yes	Yes	Compare post-BL Urine Blood (Dipstick) toxicity grade to BL Urine Blood (Dipstick) toxicity grade. If post-BL toxicity is greater than BL toxicity, then treatment-emergent
No	-	Yes	No	Treatment-emergent. Use post-BL Urine Blood (Dipstick) toxicity grade.
No	-	No	-	Do not count subject in the denominator for "Urine RBC

		(Hematuria, Quantitative or Dipstick)"
		2 ipstivii)

BL = Baseline. Quant = Quantitative. "-" means any value can be present (or it can be missing), as it does not affect the classification

18) Concomitant nonstudy-drug ARV medications (ie, ARV medications other than study drug that are taken while receiving study drug) will be flagged in "Nonstudy-Drug Antiviral Medication" listing. The logic to define concomitant nonstudy-drug ARV is similar to concomitant non-ARV Medications (see details in Section 7.4.2)

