For all eligible subjects, blood and urine will be collected at Day 1, Weeks 4, 8, 12, and then every 12 weeks through the End of Blinded Treatment Visit. Laboratory analyses (hematology, chemistry, and urinalysis), HIV-1 RNA, CD4+ cell count and percentage, and complete or symptom-directed physical examinations will be performed at the Screening, Day 1, and all subsequent study visits.

Adverse events and concomitant medications will be assessed at each visit.

Historical HIV-1 RNA genotypes (from resistance testing) will be collected, if available.

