Tenofovir (TFV) is a nucleotide analog that inhibits HIV-1 reverse transcription. While tenofovir disoproxil fumarate (TDF), an oral prodrug of TFV, is a preferred NtRTI for initial therapy, nephrotoxicity is an identified risk, and reductions in bone mineral density (BMD) have been shown that are larger than those seen with other nucleoside/nucleotide reverse transcriptase inhibitor (NRTIs). Tenofovir alafenamide (TAF) is also an oral prodrug of TFV. TAF is more stable in plasma than TDF, provides higher intracellular levels of the active phosphorylated metabolite tenofovir diphosphate (TFV-DP), and approximately 90% lower circulating levels of TFV relative to TDF at the clinical doses. The distinct metabolism of TAF offers the potential for an improved clinical profile compared with TDF.

Bictegravir (BIC) (previously referred to as GS-9883) is a potent inhibitor of HIV-1 integrase that is being evaluated for the treatment of HIV-1 infection. Antiviral testing has shown that BIC is active against a broad panel of HIV-1 viral lab strains and clinical isolates. BIC is fully active against a panel of mutant viruses with resistance to NRTIs, non-nucleoside reverse-transcriptase inhibitors (NNRTIs), and protease inhibitors (PIs). Integrase mutant viruses that are resistant to the INSTIs raltegravir (RAL) and elvitegravir (EVG) remain largely sensitive to BIC.

Gilead Sciences (Gilead) has coformulated BIC with the NRTI emtricitabine (FTC; F) and the NtRTI TAF into an FDC tablet that is suitable for once-daily use. This bictegravir/emtricitabine/tenofovir alafenamide (B/F/TAF) FDC may provide a potent, convenient, tolerable, and practical regimen for the long-term treatment of patients with HIV infection.

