Total Amylase	> 1.0 to 1.5 × ULN	> 1.5 to 2.0 × ULN	> 2.0 to 5.0 × ULN	> 5.0 × ULN
Pancreatic Amylase	> 1.0 to 1.5 × ULN	> 1.5 to 2.0 × ULN	> 2.0 to 5.0 × ULN	> 5.0 × ULN
Lipase	> 1.0 to 1.5 × ULN	> 1.5 to 3.0 × ULN	> 3.0 to 5.0 × ULN	> 5.0 × ULN
Albumin	-	2.0 to < LLN g/dL	< 2.0 g/dL	NA
Pediatrics <16 years		20 to < LLN g/L	< 20 g/L	
≥ 16 years	3.0 g/dL to < LLN	2.0 to < 3.0 g/dL	< 2.0 g/dL	NA
-	30 g/L to < LLN	20  to < 30  g/L	< 20 g/L	

URINALYSIS					
	Grade 1	Grade 2	Grade 3	Grade 4	
Hematuria (Dipstick)	1+	2+	3-4+	NA	
Hematuria (Quantitative) See Note below Females	>ULN - 10 RBC/HPF	> 10-75 RBC/HPF	> 75 RBC/HPF	NA	
Males	6-10 RBC/HPF	> 10-75 RBC/HPF	> 75 RBC/HPF	NA	
Proteinuria (Dipstick)	1+	2–3+	4+	NA	
Proteinuria, 24 Hour Collection  Adult and Pediatric ≥ 10 Years  Pediatric > 3 Mo to < 10 Years	200 to 999 mg/24 h 201 to 499 mg/m  /24 h	>999 to 1999 mg/24 h >499 to 799 mg/m  /24 h	>1999 to 3500 mg/24 h >799 to 1000 mg/m²/24 h	> 3500 mg/24 h > 1000 mg/ m²/24 h	
Glycosuria (Dipstick)	1+	2-3+	4+	NA	

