## 7.2.2. Graded Laboratory Values

The Gilead Grading Scale for Severity of Adverse Events and Laboratory Abnormalities will be used for assigning toxicity grades (0 to 4) to laboratory results for analysis. Grade 0 includes all values that do not meet the criteria for an abnormality of at least Grade 1. For laboratory tests with criteria for both increased and decreased levels, analyses for each direction (ie, increased, decreased) will be presented separately.

If there is any laboratory toxicity grading scale overlapping with the normal reference ranges (eg, grade 1 scale overlaps with normal reference ranges), laboratory values that are within the normal range will be grade 0 except for lipid tests.

For triglycerides, LDL, and cholesterol, the protocol specified toxicity grading scale is for fasting test values, so non-fasting lipid results (or lipid results without known fasting status) will not be graded or summarized by toxicity grades.

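### SAP Appendix 8 item 17 leaves urine protein out of the graded laboratory abnormality outputs without a reason, in conflict with SAP 7.2.2.2 and protocol 8.6.3

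*SAP*

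**What the plan says.** **Protocol.** The urinalysis part of the Appendix 4 severity scale covers three conditions: hematuria, proteinuria and glycosuria. Proteinuria has two entries. One is a row whose label starts "Proteinuria (Dipstick", with Grade 1 at 1+, Grade 2 at 2–3+, Grade 3 at 4+ and no Grade 4. The other is "Proteinuria, 24 Hour Collection", for which the visible schedule shows no sample. The synopsis schedules "Laboratory analyses (hematology, chemistry, and urinalysis), HIV-1 RNA, CD4+ cell count and percentage" at Screening, Day 1 and all later visits, and Appendix 2 marks urinalysis in every visit column. Section 8.6.3 says that graded abnormalities follow Appendix 4 and that the maximum postbaseline grade is summarised for each laboratory parameter.

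**SAP, main text.** Section 7.2.2 says the Gilead scale "will be used for assigning toxicity grades (0 to 4) to laboratory results for analysis". Section 7.2.2.2 plans treatment-emergent summaries by laboratory test and treatment group, for both the Safety Analysis Set and the All B/F/TAF Analysis Set. Neither section excludes urine protein. Section 7.8 declares no change from the protocol's safety analyses.

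**SAP, Appendix 8.** Item 17 introduces its table with "The following labels will be used for treatment-emergent laboratory abnormalities and treatment-emergent Grade 3 or 4 laboratory abnormalities summary tables and listings". The urinalysis block has three rows: urine blood by dipstick, urine glucose, and quantitative urine RBC. The first and third share one table label.

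**The concern.** Appendix 8 is the programming specification, so item 17 is the list a programmer will follow when building the graded tables. A test that is graded in the protocol, but has no row there, is likely to be left out of them.

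The secondary objective is safety and tolerability, and these tables are where laboratory toxicity is compared between arms. Leaving urine protein out would have two effects. There would be no frequency of graded proteinuria by arm. The overall count of subjects with any treatment-emergent graded abnormality would also miss those whose only such abnormality was proteinuria.

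No other SAP output fills the gap by arm. The renal section, 7.2.5, covers serum creatinine and eGFR only.

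**Working it through.** There is no plan figure to reproduce. The check is a comparison of texts.

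**Step 1: count the rows in item 17.** There are 4 hematology, 26 chemistry and 3 urinalysis rows, so 4 + 26 + 3 = 33. Rows for urine protein: 0.

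**Step 2: compare the urinalysis conditions graded by the protocol with item 17.**

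| Condition graded in protocol Appendix 4 | Row in SAP item 17 |
|---|---|
| Hematuria (dipstick, quantitative) | Yes, two rows under one table label |
| Glycosuria (dipstick) | Yes |
| Proteinuria (dipstick) | No |
| Proteinuria (24-hour) | No; no such sample in the visible schedule |

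Item 17 carries two of the three conditions.

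**Step 3: is proteinuria an isolated gap or one of many?** Take the blood panels in protocol 6.10.1 and Appendix 2 and look up each analyte in Appendix 4. Every listed analyte that is graded for HIV-positive adults has a row in item 17. The Appendix 4 tests without a row fall into two groups. Some are not in the study's listed panels (for example GGT, uric acid and the coagulation tests). Others are graded for HIV-negative subjects only (CD4 and lymphocyte counts). If protein is part of the urinalysis panel, it is the only collected and graded adult test left out.

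**Step 4: look for a stated exclusion.** Item 30 says calcium, phosphorous and magnesium were not tested after Day 1 unless a retest was needed, and that they therefore have no summary table. The SAP says nothing comparable about urine protein.

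**Step 5: look for another output.** SAP 7.2 plans a by-subject urinalysis listing in which values of Grade 1 or higher are flagged. That would show graded urine protein subject by subject, but it gives no rates and no comparison by arm.

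**Step 6: is protein measured?** Protocol 6.10.2 names urinalysis without listing its components. Item 17 uses dipstick blood and urine glucose from the same samples, so a dipstick protein result is likely. That remains an inference.

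**The case against.** The strongest reply is that item 17 only assigns labels and that Sections 7.2.2 and 7.2.2.2 are the operative text. Those sections cover laboratory tests generally, so proteinuria would be tabulated anyway. Item 17 is also an imperfect guide to which tables exist: it has rows for corrected calcium, magnesium and phosphate, although item 30 says those tests get no summary table. Further, an abnormality that needs intervention or leads to study drug interruption must be recorded as an adverse event (protocol 7.1.3), and adverse events are tabulated by arm. All of this stands. It shows that the SAP conflicts with itself; it does not show which text the programmer will follow.

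Four stronger readings are tempting, and the documents do not support them.

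- *A reader might infer that graded proteinuria is lost altogether.* The main text still promises it by test, and the urinalysis listing would flag it.
- *A reader might infer that proteinuria is the only collected renal marker free of the creatinine-secretion effect*, which protocol 1.2.3.1 presumes to act through OCT2. BUN is collected, graded and has a row in item 17, and it is not derived from creatinine.
- *A reader might infer an expected arm difference from the protocol's remark that* "nephrotoxicity is an identified risk". That remark concerns TDF. Both arms receive TAF 25 mg, for which Section 1.1 gives about 90% lower circulating tenofovir, so tenofovir exposure does not separate the arms.
- *A reader might put a number on the loss.* An assumed incidence of 5–15% would give 0.05 × 565 = 28 to 0.15 × 565 = 85 subjects, but neither document gives an incidence. Nor is this the effect on the any-abnormality count. In the Phase 2 study 84.4% and 87.5% of subjects already had at least one abnormality, leaving 15.6% and 12.5% without. If those rates applied here and events were independent, the newly counted subjects would number about 28 × 0.125 = 4 to 85 × 0.156 = 13. Every step of that rests on assumption.

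**Conclusion.** The point holds as an unexplained inconsistency. Item 17 omits urine protein, while protocol 8.6.3 and SAP 7.2.2.2 call for graded summaries by parameter or test, on a scale that grades dipstick proteinuria.

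The consequence is conditional. It arises if the outputs are programmed from item 17 as written and if urine protein was measured. Some schedule rows are redacted, so a separate urine test cannot be ruled out either. The size cannot be stated from the documents.

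This is a minor correction to safety reporting. It has no bearing on the primary or secondary efficacy analyses.

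**What to change.** Add one row to the urinalysis block of item 17: listing label *Urine Protein*, toxicity direction *Increase*, table label *Urine Protein (Proteinuria)*. Carry it into the treatment-emergent and Grade 3–4 summaries and listings for both the randomized phase and the All B/F/TAF analyses.

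If protein was not part of the urinalysis panel, or is left out on purpose, say so and give the reason in the style of item 30.

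The cost is one table row or one sentence. If protein is in the panel, no new data are needed. The SAP governs the final analysis and is to be finalised before the database is. After that, its Section 1 requires any change to be documented in the clinical study report.

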# 19) Lipid modifying medication analyses:

- Lipid modifying medication is defined to be the concomitant medication with WHO Drug ATC2 term (drug class) = "LIPID MODIFYING AGENTS" and WHO Drug preferred drug name (CMDECOD) contains wording of "STATIN" in the ADCM dataset.
- Subjects who took lipid modifying medications at study entry refer to the subjects who have any use of the lipid modifying agents at study day 1 (ie, the first dose date) for randomized phase analysis.
  - a) More specifically, subjects with "Lipid Modifying Agent Use at Study Entry" include those subjects in safety analysis set for randomized phase analysis with meeting both the following criteria: 1) any selected CM record with the start date ≤ the first dose date for randomized phase analysis, and 2) the end date of the selected CM record ≥ the first dose date or the end date of the selected CM record is ongoing
  - b) For lipid modifying medications with the start date completely unknown, we assume the start date is on or before the first dose date, lipid modifying medication was considered as being taken at study entry if the end date is not prior to the first dose date (ie, the end date is on or after the first dose date, completely unknown, or ongoing).
  - c) Lipid modifying medications with the start date prior to the first dose date for randomized phase analysis and the end date unknown (completely missing) were considered as being taken at study entry (the unknown end date is assumed on or after the first dose date).
- Subjects who initiated lipid modifying medications during the study for randomized phase analysis refer to the subjects in the safety analysis set who didn't take lipid modifying medications at study entry and with any selected CM record started after the first blinded study drug dose date and on and prior to the last blinded study drug dose date.
- Subjects who took lipid modifying medications at first dose of B/F/TAF (including both phases) refer to the subjects who use of the lipid modifying agents at study day 1 of all B/F/TAF analysis. More specifically, subjects with "Lipid Modifying Agent Use at

First Dose of B/F/TAF" include those subjects in All B/F/TAF Analysis Set with: 1) any selected CM record with the start date ≤ the first dose date of B/F/TAF (including both phases), and 2) the end date of the selected CM record is ongoing or the end date of the selected CM record ≥ the first dose date of B/F/TAF (including both phases).

- a) For lipid modifying medications with start date completely unknown, we assume the start date is on or before the first dose date of B/F/TAF (including both phases), lipid modifying medication was considered as being taken at first dose of B/F/TAF (including both phases) if the end date is not prior to the first dose date of B/F/TAF (including both phases) (ie, the end date is on or after the first dose date of B/F/TAF (including both phases), completely unknown, or ongoing).
- b) Lipid modifying medications with the start date on or prior to the first dose date of B/F/TAF (including both phases) and the end date completely unknown were considered as being taken at first dose of B/F/TAF (including both phases).
- Subjects who initiated lipid modifying medications while subject receiving B/F/TAF includes the following subjects in the All B/F/TAF Analysis Set: (1) for subjects who permanently discontinued study drug with any selected CM record started after the first dose date of B/F/TAF (including both phases) and on or prior to last dose of B/F/TAF (including both phases). (2) for subjects who meet criteria (1) above, if they took lipid modification medications at first dose of B/F/TAF (including both phases), or if they took lipid modifying medications on or after randomized phase first dose and before first dose of B/F/TAF, they will NOT be considered initiated lipid modifications while receiving B/F/TAF for the all B/F/TAF analysis.
- 20) For figures, if at a visit where n (sample size) for any treatment group <= 5, data for that treatment group will not be displayed at the visit in figure (except the Kaplan-Meier figure), but all data will be included in the corresponding table summary.
- 21) Vital signs and weight, height, BMI will be in the same listing.

## 22) HIV/HBV and HIV/HCV Coinfection:

• The following table presents the HBV and HCV tests with all possible values. Values that have an asterisk after them denote a "positive" (or "quantifiable" for HBV DNA and HCV RNA) result while all others denote a "negative" result.

Label	LBTESTCD	LBTEST	Possible Values
HBsAg	ATT1	Hep.B Surf.Ag Quant(-70)CL	NUMERICAL VALUE or "<0.05" or ">124925.00" (IU/mL)
HBsAg	ATT2	Hep. B Surf. Ag Qual(-70)-CL	"Repeat reactive, confirmed"*, "Repeat Reactive Unconfirmed", "Non-Reactive"
HBsAb	CNT353	anti-Hep B Surface Ag2 Qual	"Positive"*, "Negative"
HBcAb	CNT68	Hepatitis B Core Total	"Positive"*, "Negative"
HBV DNA	GET1883	HBV DNA CAP/CTM 2.0-EDTA-CL	"No HBV DNA detected", "<20 IU/mL HBV DNA detected", ">170000000"*, NUMERICAL VALUE (IU/mL)*
HBV DNA	GET1884	HBV DNA CAP/CTM 2.0Dil- EDTA-CL	NUMERICAL VALUE (IU/mL)*
HCVAb	CNT350	Hepatitis C Virus Antibody	"Positive"*, "Indeterminate", "Negative"
HCV RNA	GET1881	HCV RNA CAP/CTM 2.0EDTA-CL	"No HCV RNA detected", "<15 IU/mL HCV RNA detected", NUMERICAL VALUE (IU/mL)*

Note: HBVDNA AMPLIPREPTAQMAN 2.0 DIL(GET1884) is for HBV DNA CAP/CTM 2.0 >170,000,000 IU/mL. HBsAg(ATT1) test is conducted when HBsAg(ATT2) when ATT2 results = "Repeat reactive, confirmed", "Repeat Reactive Unconfirmed". Only HBsAg (ATT2) results will be summarized for HBV surface antigen.

- For baseline coinfection, when considering the different laboratory tests, take the latest, non-missing record on or prior to the first dose date defined for randomized phase analysis or all B/F/TAF analysis for each test (eg, HBsAg, HBsAb, HBcAb, and HBV DNA)
  - The baseline coinfection status will be one of the three values: Yes/No/Null
  - The following tables provide combinations of HBV and HCV tests and the corresponding baseline coinfection status

HBsAg	HBsAb	HBcAb	HBV DNA	Coinfection Status
Positive	-	-	-	Y
	Positive	-	-	N
			Quantifiable	Y
		Positive	Not Quantifiable	N
		Γ	Missing	Null
	Negative	Negative	-	N
			Quantifiable	Null
		Missing	Not Quantifiable	N
Negative		Γ	Missing	Null
			Quantifiable	Null
		Positive	Not Quantifiable	N
			Missing	Null
	Missing	Negative	-	N
			Quantifiable	Null
		Missing	Not Quantifiable	N
			Missing	Null
	Positive	-	-	Null
			Quantifiable	Y
		Positive	Not Quantifiable	Null
Missing	Negative		Missing	Null
		Negative	-	Null
		Missing	-	Null
Γ	Missing	-	-	Null

HCVAb	HCV RNA	Coinfection Status
	Quantifiable	Y
Positive	Not Quantifiable	N
	Missing	Null
Negative	-	N
	Quantifiable	Null
Missing	Not Quantifiable	N
	Missing	Null

"-" means any value can be present, as it does not affect the classification

- For incident coinfection, all laboratory tests must share the same accession number and if any set of values meets the criteria, then the subject is considered to have incident coinfection
  - The incident coinfection status will be one of two values: Yes/Null
  - The following tables provide combinations of HBV and HCV tests that are considered "Y" for incident coinfection status (all others are considered Null)

HBsAg	HBsAb	HBcAb	HBV DNA	Coinfection Status
Positive	-	-	-	Y
Negative	Negative	Positive	Quantifiable	Y
Missing	Negative	Positive	Quantifiable	Y

HCVAb	HCV RNA	Coinfection Status
Positive*	-	Y
-	Quantifiable	Y

\* Subjects with positive HCVAb postbaseline must also have negative or missing HCVAb at baseline in order to be considered as having incident HIV/HCV coinfection.

- For adverse events, the start date must be after the first dose date and on or prior to the last dose date for randomized phase analysis.
- For incomplete AE start dates, please follow the logic specified in Section 7.1.5.2, but modify the second criterion to read, "The month and year (or year) of the AE onset is the same as or before the month and year (or year) of the date of the last dose of study drug for randomized phase analysis".
- 23) HBV DNA test codes: If the result of the laboratory test code GET1883 (HBV DNA CAP/CTM 2.0-EDTA-CL) is listed as ">170000000", then a reflexive test code GET1884 (HBV DNA CAP/CTM 2.0Dil-EDTA-CL) should be performed and will share the same accession number as the original GET1883 test. In this instance, use the result from GET1884 instead of GET1883 when determining HBV DNA.
- 24) Reasons for Subjects who excluded from Week 48 PP Analysis Set will be summarized as follows in table:
  - a) Did Not Have On-Treatment HIV-1 RNA in Week 48 Window Unless due to Discontinuation of Study Drug for Lack of Efficacy
  - b) Did Not Meet the Criteria of Taking DTG + F/TAF, or DTG + F/TDF for the Protocol-defined Duration Before the screening visit
  - c) Did Not Meet the Criterion of HIV-1 RNA < 50 copies/mL for the Protocol-defined Duration Before screening visit
  - d) Did Not Meet the Criteria of HIV-1 RNA < 50 copies/mL at screening visit
  - e) Did Not Meet the Criteria of Having no Resistance to INSTIs or Confirmed Virologic Failure

"-" means any value can be present, as it does not affect the classification

- f) Did Not Meet the Criteria of Having only the Protocol Permitted Historical ARV resistance
- g) Took Protocol Prohibited Medications
- h) Adherence Rate for Active Study Drug up to Week 48 Visit Below the 2.5th Percentile
- 25) The number of decimal places in reporting p-values should be as follows:
  - a) values less than  $0.0001 \rightarrow < 0.0001$
  - b) values greater than  $0.0001 \rightarrow$  round to 4 decimal places
- 26) In this study, only 3rd generation LDL is collected.
- 27) For nonstudy-drug ARV listing, ARVs which were dosed between the first dose date and the last dose date (inclusive) of study will be flagged (eg, ^). However, please note, if CM end date is completely missing and it's not ongoing and CRF said it's a 'Prior ARV', the ARV will not be flagged.
- 28) Study and/or study drug discontinuations due to COVID-19
  - a) Study Drug Discontinuation
    - Run NLP algorithm on the comment field from Study Drug Completion eCRF, checking for "COVID-19" text
    - In COCOVID19 data set if COFORM = "Study Drug Completion", then subject discontinued study drug due to COVID-19
    - If study drug discontinued due to an AE, check if corresponding AE flagged as a COVID-19
  - b) Study Discontinuation
    - Run NLP algorithm on the comment field from general comments for "COVID-19" text
    - In COCOVID19 data set if COFORM = "Study Completion", then subject discontinued study due to COVID-19
    - If study discontinued due to an AE, check if corresponding AE flagged as a COVID-19

